--	---

	
 • Patient who has a renal function impairment with estimated glomerular filtration rate (GFR) <30 mL/min/1.73 m² (using MDRD formula) or end-stage renal disease; • Contraindication to use of insulin glargine, or lixisenatide or GLP-1 receptor agonist (Victoza®, Byetta®, Bydureon®, Tanzeum®/ or Trulicity®) according to local labeling; • Any contraindication to metformin or pioglitazone or SGLT2 inhibitors (when applicable) use, according to local labeling; • History of hypersensitivity to insulin glargine, or to any of the excipients; • History of allergic reaction to any GLP-1 receptor agonist or to Metacresol; • Personal or immediate family history of medullary thyroid cancer (MTC) or genetic condition that predisposes to MTC (eg, multiple endocrine neoplasia type 2 syndromes); • History of pancreatitis (unless pancreatitis was related to gallstones and cholecystectomy was already performed), chronic pancreatitis, pancreatitis during a previous treatment with incretin therapies, pancreatectomy; • Body Mass Index (BMI) ≤20 or >40 kg/m².

Main selection criteria for the extension period
	
Inclusion criteria:
 
 • Patients treated with FRC during the 26-week randomized treatment period. 
Exclusion criteria:
 
 • Patients in the FRC arm receiving rescue therapy and HbA1c >8% at Week 22; • Patients in the FRC arm who discontinued prematurely from FRC treatment before Week 26; • Patients in the GLP-1RA treatment arm after randomization.

Total expected number of patients
	
Approximately 500 patients randomized in the study (250 patients per group) during the open-label randomized treatment period.
 
Approximately 230 patients are estimated to enter the single-arm extension period with the treatment of FRC.

STUDY TREATMENT(s)	

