
STATISTICAL CONSIDERATIONS
	
Sample size determination:
 
A sample size of 250 patients per group will provide 90% power to detect a difference of 0.4% in the HbA1c change from baseline to Week 26 between the FRC and GLP-1 receptor agonist arm. This calculation assumes a common standard deviation of 1.1% at the 5% significance level (2-sided) and a common drop-out rate of 20% at 26 weeks. It is based on the intent-To-Treat (ITT) analysis and also assumes in the conservative manner that the FRC dropped patients will respond as the control patients, ie, no treatment difference between FRC dropped patients and the control patients.
 
Analysis population:
 
The primary efficacy population will be the modified Intent-To-Treat (mITT) population, which includes all randomized patients who have a baseline assessment and at least one post-baseline assessment of any primary or secondary efficacy endpoints, irrespective of compliance with the study protocol and procedures. Patients will be analyzed in efficacy analyses by the treatment regimen allocated by interactive response technology (IRT) according to the randomization schedule at randomization visit (as randomized).
 
The safety analysis will be conducted on the safety population, defined as all randomized patients exposed to at least one dose of investigational medicinal product, regardless of the amount of treatment administered. Patients will be analyzed according to the treatment regimen actually received.
 
Primary efficacy endpoint analysis:
 
Analyses of the primary efficacy endpoint (change from baseline to Week 26 in HbA1c) will be performed using the mITT population, using HbA1c values obtained from the scheduled visits during the 26-week randomized treatment period, including those obtained after IMP discontinuation or rescue medication use.
 
The statistical test will be two-sided at the alpha level of 0.05.
 
The primary analysis method for the primary efficacy endpoint will be a mixed-effect model with repeated measures (MMRM) under the missing at random framework. The MMRM model will include the treatment groups, randomization

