7.2.5 Exclusion criteria for the extension period

- E 34. Patients in the FRC arm with a rescue therapy and HbA1c >8% at Week 22;
- E 35. Patients in the FRC arm who discontinued prematurely from FRC treatment before Week 26;
- E 36. Patients in the GLP-1RA treatment arm after randomization.

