8.4 METHOD OF ASSIGNING PATIENTS TO TREATMENT GROUP

Patients will be randomized to one of the two following treatment arms during the 26-week open-label treatment period:

- FRC once daily, or
- Victoza® once daily, Byetta® twice daily, Bydureon® once weekly, Tanzeum® once weekly, or Trulicity® once weekly (continuing whichever therapy they were taking prior to randomization).

The randomization ratio is 1:1. The randomization is stratified by HbA1c (<8%, ≥8%) at screening and GLP-1 receptor agonist subtype at screening (once/twice daily formulations, once weekly formulations).

The randomization and the treatment allocation are performed centrally by an interactive response technology (IRT). The randomized treatment kit number list is generated centrally by Sanofi, and the Study Biostatistician provides the randomization scheme (including stratification) to the IRT. Then, the IRT generates the patient randomization list according to which it allocates treatment groups to the patients.

The IMPs (FRC, or Victoza®, or Byetta®, or Bydureon®, or Tanzeum®, or Trulicity®) will be provided starting at V3 in open-label boxes and are identified with treatment kit numbers.

At the screening visit the Investigator or designee has to contact the IRT center to receive the patient number. The patient identification (patient number) is composed of a 12-digit number containing the 3-digit country code, the 4-digit center code and the 5-digit patient chronological number (which is 00001 for the first patient screened in a center, 00002 for the second patient screened in the same center, etc).

A patient cannot be randomized more than once in the study.

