11 STATISTICAL CONSIDERATIONS

11.1 DETERMINATION OF SAMPLE SIZE

The sample size calculations are based on the primary efficacy variable change in HbA1c from baseline to Week 26 and intent-to-treat (ITT) analysis, with the following assumptions:

- A common standard deviation of 1.1%;
- A 0.4% mean difference between FRC and GLP-1 receptor agonist in change in HbA1c from baseline to Week 26;
- A drop-out rate of 20%; The FRC dropped patients are assumed to respond the same as the control patients, ie, no treatment difference between the FRC dropped patients and the control patients;
- A t-test at a 2-sided 5% significance level with at least 90% power.

Based on the above assumptions, 500 patients (250 per group) are needed for this study.

Calculations were made using nQuery Advisor® 7.0.

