1.3 DETERMINATION OF SAMPLE SIZE

[figure not shown]
The sample size calculations are based on the primary efficacy variable change in HbA1c from baseline to Week 26 and ITT analysis, with the following assumptions:

- A common standard deviation of 1.1%,
- A 0.4% mean difference between FRC and GLP-1 receptor agonist in change in HbA1c from baseline to Week 26,
- A drop-out rate of 20%. The patients in the FRC group who discontinued treatment are assumed to respond the same as the control patients, i.e., no treatment difference between the patients in the FRC group who discontinued treatment and the control patients
- A t-test at a 2-sided 5% significance level with at least 90% power.

Based on the above assumptions, 500 patients (250 per group) are needed for this study.

Calculations were made using nQuery Advisor® 7.0.

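### Does the estimate of about 230 extension entrants contradict the 20% drop-out behind the sample size?

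*Protocol*

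**What the plan says.** The protocol synopsis, under the total expected number of patients, gives 250 patients per group and then "Approximately 230 patients are estimated to enter the single-arm extension period with the treatment of FRC". It does not show how the figure was obtained.

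The sample size text uses a drop-out rate. The synopsis assumes "a common drop-out rate of 20% at 26 weeks". Protocol section 11.1 lists "A drop-out rate of 20%; The FRC dropped patients are assumed to respond the same as the control patients" and concludes "Based on the above assumptions, 500 patients (250 per group) are needed for this study". SAP section 1.3 repeats the rate and is more specific about who the drop-outs are: "The patients in the FRC group who discontinued treatment are assumed to respond the same as the control patients".

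Entry to the extension is limited by Protocol section 7.2.5. E 35 excludes "Patients in the FRC arm who discontinued prematurely from FRC treatment before Week 26", and E 34 excludes FRC patients who have rescue therapy and still have HbA1c above 8% at Week 22. Protocol section 10.1.3.1 also requires consent to continue.

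**The concern.** Put together, these statements seem to conflict. If 20% of FRC patients stop treatment before Week 26 and every one of them is excluded from the extension, about 200 remain, and E 34 and refusals can only lower that number. An entry of 230 leaves room for 8% loss from all causes together. One of the two figures therefore looks mistaken.

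If the 230 is too high, the extension gives less one-year information on safety, immunogenicity and pharmacokinetics than a reader of the synopsis would expect. If the 20% is too high, the trial is larger than its primary comparison needs.

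**Working it through.** **Inputs.** 250 per group, 1:1 allocation, difference 0.4%, SD 1.1%, two-sided 5% t-test with a minimum of 90% power, and 20% drop-out (Protocol synopsis and sections 8.4 and 11.1; SAP section 1.3). Extension entry of 230 (Protocol synopsis).

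**1. Reproduce the sample size.** FRC drop-outs are given the control response, so the effect is diluted:

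0.4 x (1 - 0.20) = 0.32

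n per group = 2 x (1.960 + 1.282)² x 1.1² / 0.32² = 249 by the normal approximation, and 250 by the noncentral t. Power at 250 per group is 90.1% (noncentral t). The stated 250 is confirmed.

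The alternative reading, in which drop-outs are lost and the number is inflated, gives 159 / 0.80 = 199, which does not match. The 20% is therefore a dilution rate: these patients stay in the analysis with no treatment effect. This agrees with the SAP's description of them as treatment discontinuers.

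**2. Compare with the extension figure.**

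- Expected to remain on treatment at 20% loss: 250 x 0.80 = 200.
- Retention implied by 230: 230 / 250 = 92%, so 8% loss.
- FRC patients needed for 230 entrants at 20% loss: 230 / 0.80 = 287.5, so 288.
- If the true loss were 20%, the binomial probability that 230 or more of 250 remain is about 1.4 x 10⁻⁷.

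So 230 was not obtained from the 20% rate, and the word approximately does not cover the gap.

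**3. Effect on the primary comparison if 8% is the better forecast.**

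0.4 x (1 - 0.08) = 0.368. Power at 250 per group is 96.2%, and 189 per group would give 90%. The specified minimum is met with room to spare.

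**4. Effect on the extension if 20% is the better forecast.**

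| Quantity | 230 entrants | 200 entrants |
|---|---|---|
| One-sided upper 95% bound when no event is seen, 1 - 0.05^(1/n) | 1.29% | 1.49% |
| Chance of at least one case of an event with true rate 1%, 1 - 0.99^n | 90.1% | 86.6% |

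The 1% rate is only an illustration; the documents set no such target.

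**5. Look for anything that depends on 230.** The sample size sections of both documents do not use it. The testing hierarchy in SAP section 2.4.4.3 contains Week 26 endpoints only. For the extension, SAP section 2.4.4.2 plans descriptive statistics, counts and percentages in the FRC group, and SAP section 2.4.5 plans no testing of safety variables. No precision target or minimum number is attached to the extension.

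**The case for a change.** The strongest case for a change is that the drop-outs in the power calculation and the patients excluded by E 35 are the same people. The SAP's wording and the arithmetic in step 1 both show it, so the mismatch cannot be explained by two meanings of drop-out. The synopsis gives the only stated size for the extension, no retention assumption accompanies it, and one sentence would settle the matter. It can be added that the word conservative in the synopsis refers to how dropped patients respond, not to the 20% itself, so the plan does not say that 20% was chosen to be cautious.

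All of this stands as description. It does not show that either figure is wrong. A rate used for power and a forecast used for planning the extension serve different purposes, and it is ordinary to be pessimistic in the first and realistic in the second. That this was the intention here is an inference; the documents neither confirm nor contradict it. Nor is 200 a ceiling. It is the expected number if the 20% rate comes true, and more patients may enter if retention is better. Stating it as a maximum would turn a power assumption into a limit that the design does not impose.

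**Conclusion.** The mismatch is real but has no consequence for the trial. At 20% loss about 200 FRC patients would be expected to enter the extension, before E 34 exclusions and refusals, against a forecast of 230. The difference is 30 patients, or 13% of the forecast (30 / 230). Both figures can stand if the 20% is a cautious power input and the 230 a separate forecast with about 92% retention.

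The primary test is sound under either rate: 90.1% power at 20% loss and about 96% at 8%. The extension analyses are descriptive and will be reported on however many patients enter, so nothing that is done or concluded depends on the forecast. Writing down the retention assumption behind 230 would help a careful reader, but it would not alter any procedure, analysis or inference. The point is a missing explanation and no change to the plan is needed. This rests on the plan's own SD, difference and dilution rule, and on no E 34 or refusal rate, since none is given.

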1 FLOW CHARTS

1.1 GRAPHICAL STUDY DESIGN

* Additional titration phone calls – only for FRC arm

** Insulin glargine/lixisenatide fixed ratio combination (FRC) treatment will be initiated with the Peach Pen. The initial daily dose to be administered will be 10 U; this corresponds to an initial associated dose of insulin glargine 10U and lixisenatide 5 µg according to the 2 U/1 µg fixed ratio used in the Peach Pen. Afterwards, doses will be individually titrated throughout the study to reach and maintain fasting SMPG: 80-100 mg/dL (4.4-5.8 mmol/L) avoiding hypoglycemia.

† Liraglutide, exenatide, albiglutide, or dulaglutide is discontinued at visit 3 for patients randomized to the FRC treatment. Any patient treated with a once weekly GLP-1 RA upon entering the study who is assigned to receive the FRC treatment should not receive their first dose until at least 1 week after their last dose of GLP-1 RA.

1.2 STUDY FLOW CHART

	Screening period		Randomized treatment period ^b																									Post-treatment follow-up ^c			
VISIT ^a	1	2	3	4	5	6	7	8	9	10	11	12	13	14	15	16	17	18	19	20	21	22	23	24	25	26	27	28 ^d	follow-up		
WEEK	-2	-1	0	0.5 ^e	1	1.5 ^e	2	2.5 ^e	3	3.5 ^e	4	4.5 ^e	5	5.5 ^e	6	6.5 ^e	7	7.5 ^e	8	10	12	14	16	18	20	22	24	26			
Informed Consent	X																														
Inclusion/Exclusion Criteria	X		X																												
Medical, surgical, and diabetes histories, alcohol & smoking habits, demography, prior medications	X																														
Physical Examination	X																												X		
Height	X																														
Body weight	X		X								X									X		X				X			X		
Vital Signs (heart rate, blood pressure)	X	X	X				X				X								X		X				X				X		
12-lead ECG	X																												X		
Diet and Lifestyle counseling			X (once at V2 or 3)																			X							X		
IRT contact	X		X				X				X								X		X				X		X		X	X	
Randomization			X																												
Concomitant medication recording	Continuously assessed and recorded all along the study																														
AE/SAE/Symptomatic Hypoglycemia ^f	Continuously assessed and recorded all along the study																														
Glucometer dispensation & training (including training on glucose measurements) ^g		X																													
Diary dispensation / collection (reviewed at each on-site visit)		X	X				X				X								X		X				X		X		X		

VISIT ^a	Screening period		Randomized treatment period ^b																									Post-treatment follow-up ^c			
	1	2	3	4	5	6	7	8	9	10	11	12	13	14	15	16	17	18	19	20	21	22	23	24	25	26	27	28 ^d	follow-up		
WEEK	-2	-1	0	0.5 ^e	1	1.5 ^e	2	2.5 ^e	3	3.5 ^e	4	4.5 ^e	5	5.5 ^e	6	6.5 ^e	7	7.5 ^e	8	10	12	14	16	18	20	22	24	26			
Pen-injector and self-injection training ^g			X																												
Fasting SMPG measured every day before breakfast			X	X	X	X	X	X	X	X	X	X	X	X	X	X	X	X	X												
Fasting SMPG measured at least three times per week before breakfast																				X	X	X	X	X	X	X	X	X	X		
Titration phone calls (FRC arm only) ^e				X		X		X		X		X		X		X		X													
7-point SMPG profiles (on 2 different days in the week prior to the visit) ^h			X																		X								X		
IMPs dispensation ⁱ			X				X				X								X		X			X		X					
Recording of GLP-1 receptor agonist daily/weekly dose (mg or µg) (control arm)	X	X	X		X		X		X		X		X		X		X		X		X		X		X		X		X		
Recording of FRC dose (U)			X	X	X	X	X	X	X	X	X	X	X	X	X	X	X	X	X	X	X	X	X	X	X	X	X	X	X	X	
Count returned pens							X				X								X		X			X		X		X			
Compliance check			X				X				X								X		X			X		X		X			
Central laboratory testing																															
HbA1c	X		X																X		X			X		X		X			
Fasting Plasma Glucose	X	X ^j	X								X								X		X					X		X ^j			
2-h standardized meal test ⁱ		X																											X		
Total-, LDL-, HDL-Cholesterol, triglycerides ^k			X																										X		
Urinalysis ^l	X	X																													
Hepatitis B surface antigen and hepatitis C antibody	X																														

VISIT ^a	Screening period		Randomized treatment period ^b																									Post-treatment follow-up ^c		
	1	2	3	4	5	6	7	8	9	10	11	12	13	14	15	16	17	18	19	20	21	22	23	24	25	26	27	28 ^d	follow-up	
WEEK	-2	-1	0	0.5 ^e	1	1.5 ^e	2	2.5 ^e	3	3.5 ^e	4	4.5 ^e	5	5.5 ^e	6	6.5 ^e	7	7.5 ^e	8	10	12	14	16	18	20	22	24	26		
Women only: FSH (if necessary to define menopausal status) ^m	X																													
Women only: serum pregnancy test (if childbearing potential)	X		X																		X								X	
Safety laboratory ⁿ hematology, serum chemistry	X		X																		X								X	
Amylase, Lipase	X		X				X				X										X								X	
Serum Calcitonin	X		X																		X								X	
Anti-lixisenatide and anti-insulin antibodies (only in FRC group) ^o			X								X ^q										X ^q							X ^r		
Total plasma lixisenatide concentration (only in FRC group) ^p			X								X										X							X		

VISIT ^a	Extension period								Post-treatment follow-up
	28a	29	30	31	32	33	34	35	follow-up ^c
WEEK	26	30	34	38	42	46	50	52	
Inclusion/Exclusion Criteria	X								
Physical Examination	X							X	
Body weight	X		X		X			X	
Vital Signs (heart rate, blood pressure)	X		X		X			X	
12-lead ECG	X							X	
Diet and Lifestyle counseling	X				X				
IRT contact	X		X		X			X	X
Concomitant medication recording	Continuously assessed and recorded all along the study								
AE/SAE/Symptomatic Hypoglycemia ^f	Continuously assessed and recorded all along the study								
Diary dispensation / collection (reviewed at each on-site visit)	X		X		X			X	
Fasting SMPG measured at least three times per week before breakfast	X	X	X	X	X	X	X	X	
7-point SMPG profiles (on 2 different days in the week prior to the visit) ^h	X							X	
IMPs dispensation ⁱ	X		X		X				
Recording of FRC dose (U)	X	X	X	X	X	X	X	X	
Count returned pens	X		X		X			X	
Compliance check	X		X		X			X	
Central laboratory testing									
HbA1c	X		X		X			X	
Fasting Plasma Glucose	X		X		X			X ^j	
2-h standardized meal test ^j	X							X	
Total-; LDL; HDL-Cholesterol, triglycerides ^k	X							X	
Women only: serum pregnancy test (if childbearing potential)	X		X		X			X	

VISIT ^a	Extension period								Post-treatment follow-up
	28a	29	30	31	32	33	34	35	follow-up ^c
WEEK	26	30	34	38	42	46	50	52	
Safety laboratory ⁿ hematology, serum chemistry	X							X	
Amylase, lipase	X		X		X			X	
Serum calcitonin	X		X		X			X	
Anti-lixisenatide and anti-insulin antibodies ^o	X							X ^r	
Total plasma lixisenatide concentration ^p	X							X	

- a During the screening period and for randomization visit a visit window of ± 3 days is acceptable, taking V1 as reference until the randomization visit (V3). During the treatment period a visit window of ± 3 days is acceptable taking V3 as reference for V5 to V19 (except for additional titration calls for fixed ratio combination treatment arms; please refer to footnote e), and a visit window of ± 5 days is acceptable from V20 to V35. A visit window of -1 day or + 3 days for the post-treatment follow-up visit is acceptable using the day of V28 and V35 respectively as reference. For patients receiving weekly GLP1-RA, the post-treatment follow-up visit is scheduled 9 days after V28 with the same visit window as for the other patients. If one visit date is changed, the next visit should take place according to the original schedule.
- b Additional phone calls for titration purposes should be scheduled as often as deemed necessary by the Investigator.
- c Post-treatment follow-up visit: This visit can be a phone call visit, or an on-site visit in case of ongoing or new adverse event during the post-treatment period, if necessary.
- d **In case of premature permanent IMP discontinuation**, patients should have a visit as soon as possible with the assessments normally planned in V28 or V35 for randomized treatment or extension period, respectively (the 2-hour standardized meal test is performed only if the patient receives the IMP on the day of the meal test). Afterwards, the patients should continue in the study up to the scheduled date of study completion. They should be followed up according to the study procedures as specified in the protocol (except for the 3 day safety post-treatment follow-up). **In case of rescue therapy**, all assessments planned in V28 or V35 for randomized treatment or extension period, respectively should be performed before starting rescue therapy, patients then continue the study treatment (including metformin \pm pioglitazone \pm SGLT2 inhibitor), and all visits and assessments should be performed as scheduled.
- e These additional titration phone calls are necessary only in the fixed ratio combination (FRC) arms during the first 8 weeks of treatment, from V3 (Week 0) to V19 (Week 8), hereafter, from V19 (Week 8) until V28 (Week 26), the dose will be adjusted as necessary to maintain this fasting SMPG target, with recommendation to evaluate the dose at least once a week. Please see [Section 8.1.4.1](#) on dose adjustment.
- f Whenever the patient feels hypoglycemic symptoms, plasma glucose should be measured by the patient (or others, if applicable), if possible. Patients should be instructed to measure plasma glucose levels prior to the administration of glucose or carbohydrate intake whenever symptomatic hypoglycemia is suspected, unless safety considerations necessitate immediate glucose/carbohydrate rescue prior to confirmation.
- g The training can be repeated as often as necessary.
- h The 7-point SMPG profile should be measured at the following 7 points: pre-prandial and 2 hours postprandial for breakfast, lunch, dinner and at bedtime.
- i Any patient treated with a **once weekly GLP-1 RA** upon entering the study who is assigned to receive FRC treatment should not receive their first dose until at least 1 week after their last dose of GLP-1 RA. For these patients baseline visit must be scheduled at least 1 week after administering their last dose of GLP1.
- j At V2 and V28 and V35, FPG and C-peptide are part of the standardized meal test. The standardized meal contains approximately 600 kcal and is composed of 50 to 55% carbohydrate, 15 to 20% protein and 25 to 30% fat. The standardized meal for all patients should be consumed within a 15-minute period.
- k LDL = low density lipoprotein, HDL = high density lipoprotein.
- l Screening urinalysis at V1: (pH, glucose, ketones, leucocytes, blood/hemoglobin, protein), Urinalysis at V2 (Albumin/creatinine ratio (1st morning urines)

- m* FSH = follicle stimulating hormone.
- n* Safety Laboratory: hematology = White blood cell count (WBC), Red blood cell count (RBC), Hemoglobin, Hematocrit, platelets, differential blood count (Neutrophils, lymphocytes, monocytes, eosinophils, basophils). Serum chemistry = total bilirubin, AST, ALT, alkaline phosphatase (ALP), creatinine, uric acid, sodium, potassium, phosphorus, calcium.
- o* Samples for antibody assessment to be taken prior to IMP injection.
- p* Total plasma concentrations of lixisenatide for patients on FRC will be assessed in the time frame from 1 to 4 hours post-injection at Day 1 of the treatment and prior to injection as well as in the time frame from 1 to 4 hours post-injection at other visits. Samples will also be taken in case of premature discontinuation from IMP or in case of rescue therapy initiation, if possible. In case of premature discontinuation, one PK sample is sufficient if the last dose of IMP is not administered at the visit.
- q* At V11 and V21, only samples for anti-lixisenatide antibody assessment.
- r* One additional sample for potential additional assessments of immunogenicity will be taken at Week 26 (if the patient completes the study after Week 26) or Week 52 (if the patient participates in the extension period) or in case of premature discontinuation.

